# LIST OF ABBREVIATIONS AND RELEVANT DEFINITIONS

ABR	ABR form (General Assessment and Registration form) is the application form
	that is required for submission to the accredited Ethics Committee (ABR =
	Algemene Beoordeling en Registratie)
AE	Adverse Event
AR	Adverse Reaction
CA	Competent Authority
ССМО	Central Committee on Research Involving Human Subjects
CV	Curriculum Vitae
DSMB	Data Safety Monitoring Board
EU	European Union
EudraCT	European drug regulatory affairs Clinical Trials GCP Good Clinical Practice
IB	Investigator's Brochure
IC	Informed Consent
IMP	Investigational Medicinal Product
IMPD	Investigational Medicinal Product Dossier
METC	Medical research ethics committee (MREC); in Dutch: medisch ethische toetsing
	commissie (METC)
(S)AE	Serious Adverse Event
SPC	Summary of Product Characteristics (in Dutch: officiële productinfomatie IB1-
	tekst)
Sponsor	The sponsor is the party that commissions the organisation or performance of the
	research, for example a pharmaceutical
	company, academic hospital, scientific organisation or investigator. A party that
	provides funding for a study but does not commission it is not regarded as the
	sponsor, but referred to as a subsidising party.
SUSAR	Suspected Unexpected Serious Adverse Reaction
Wbp	Personal Data Protection Act (in Dutch: Wet Bescherming Persoonsgevens)
WMO	Medical Research Involving Human Subjects Act (Wet Medisch-wetenschappelijk
	Onderzoek met Mensen

#### SUMMARY

**Rationale:** Improving cellular immunity by means of increasing CD4 cells is one of the goals of antiretroviral therapy in HIV, which is achieved by means of virological suppression. A certain group of patients, the so called "immunologic non responders", fail to reach an acceptable CD4 cell increase despite an adequate virologic response on antiretroviral treatment. Recently a new antiretroviral agent, maraviroc (Celsentry®), is registered for the treatment of patients infected with CCR5 tropic HIV-1 virus. However, data is available suggesting that treatment with maraviroc leads to immune recovery (increase in CD4 cells) in patients who are infected with dual/mixed tropic HIV-1 virus, in the absence of a virologic response. This suggests an alternative mechanism for immune recovery, which could be especially beneficial for this group of patients.

**Objective**: The primary objective is to confirm the hypothesis that maraviroc stimulates immune recovery; the secondary objective is to explore, by virologic and immunologic investigations, the underlying mechanisms of this hypothesis.

**Study design:** multicentre, randomized, placebo-controlled, double blind, exploratory mechanistic study.

**Study population:** HIV-1 infected patients 18 years or older, who meet the inclusion criteria. **Intervention (if applicable)**: One group receives maraviroc (dose dependent on co-medication), the other group placebo.

**Main study parameters/endpoints:** A 30% increase in CD4 cell rise in the treatment group (compared with placebo).

Nature and extent of the burden and risks associated with participation, benefit and group relatedness:

- 1. In the treatment group subjects will start with a registered antiretroviral agent (maraviroc).
- 2. During the treatment year patients will perform several study visits, probably three more compared with regular visits on the outpatient clinic.
- Each visit, blood will be drawn by venapuncture for immunologic and virologic investigations (see flow chart).

## 1. INTRODUCTION AND RATIONALE

The management of patients with HIV infection now allows for the suppression of plasma HIV RNA to  $\leq$ 50 copies/ml in the majority of antiretroviral therapy (ART)-naive patients within the first 6 months of treatment [1]. Sustained suppression of HIV-1 RNA load associated with the use of "Highly Active Antiretroviral Therapy" (HAART) results in immunologic improvement. In a large prospective cohort of treatment-naive patients, 84% achieved HIV RNA levels of <400 copies/ml within 6 months of starting ART, which corresponded to mean increases in CD4+ T-cell count of 114 cells/µl at 6 months and 181 cells/µl at 12 months [2]. Similarly, a systematic review found mean increases in CD4+ T-cell count of 123 cells/µl at 24 weeks and 160 cells/µl at 48 weeks in treatment-naive patients initiating ART [1]. In patients whose HIV RNA levels are consistently suppressed, CD4+ T-cell counts typically continue to increase for 4 years or more after treatment initiation [3].

Unfortunately, a poor immune reconstitution despite a good virological control (the so called "immunologic non responders") is relatively frequent after initiation of HAART among patients with a baseline CD4 count of <350 cells/microl, older age and the baseline immunological and virological status of the patients.

In the multicenter EuroSIDA study, 29% of patients starting ART at CD4+ T-cell counts <350 cells/µl and in whom HIV RNA load was <500 copies/ml at 6 months had a 'low' CD4+ T-cell increase (defined by an increase in CD4+ T-cell count of <50 cells/µl after 6 months or a similarly low increase up to 12 months) [6]. Likewise, in a multicenter study of subjects starting protease inhibitor (PI)-based therapy for the first time, 17.3% did not achieve an increase of ≥50 CD4+ T-cells/µl at 6 months despite suppression of HIV RNA by at least 1 log10 copies/ml or to <1,000 copies/ml. Such subjects had a higher risk of clinical progression than subjects who had a similar virological response but who did achieve an increase of ≥50 CD4+ T-cells/µl at 6 months [4].

In the Dutch Athena Cohort 17 % out of 6106 patients entered and still on HAART with a suppressed HIV RNA load had a CD4+ count < 200 T-cells/ $\mu$ I at 12 months ([name], personal communication)

A lack of CD4+ T-cell count recovery appears to be the strongest independent predictor of HIV-associated clinical events and death in patients on ART, even when compared with HIV RNA levels [4, 5].

It is now well established that in patients on HAART immune restoration (CD4+ cell increase) is determined by having undetectable HIV viral load. Deeks et al, have shown that this relates to still increased levels of T cell turnover in these patients. It is thought that (as in untreated patients infected with HIV), HIV- induced T cell activation is the driver for first naive and later memory T cell depletion (7-9). Mounting evidence has accumulated from several laboratory that immune activation, either directly by effects of HIV or by bacterial translocation due to HIV, induces massive depletion of CD4+ T memory cells from the gut (10) and gradually causes depletion of CD4 T cells in chronic HIV infection. We have observed that, although prolonged HAART is believed to abolish this systemic immune activation, after the initial steep decline in T cell activation, for years a low degree of activation and expansions of CD8 memory populations can be observed. This may be compatible with ongoing low level viral replication despite the patients having undetectable plasma HIV RNA. As also naive T cell division was observed by Ki67 expression we set out to determine the origins of the naive CD4+ T cells that had been generated in patients on long term HAART. From sophisticated analyses and modeling (using changes in TRECs, Ki67 and telomere length) it appeared that naive T cell restoration was derived from thymus, however also division of peripheral naive T cells contributed (Vrisekoop et al submitted).

Recently a new antiretroviral agent, maraviroc (Celsentry ®), has become available that inhibits HIV-1 infection by selectively binding to the CCR5 coreceptor. In the MOTIVATE 1 and 2 studies performed with maraviroc in antiretroviral experienced patients who were infected with R5 tropic HIV-1 virus, almost a doubling of CD4+ cell count was seen in patients receiving maraviroc compared to the group receiving OBR+ placebo as well as a significant virologic response.

Interestingly however, a significant increase of CD4+ cells was also seen in a randomized trial (Pfizer 1029, evaluating maraviroc vs. placebo in antiretroviral experienced patients with dual tropic (D/M) or indeterminate HIV), despite no difference in virological efficacy between placebo and maraviroc. The pathogenesis underlying this increase in CD4+ cells (despite no virologic effect) in patients infected with dual tropic HIV-1 virus using maraviroc is currently not known. However these data suggests dat other immunological and/or virological mechanisms could be involved in the increase of CD4 cells caused by maraviroc, compared with other antiretroviral agents. Moreover, previous studies investigating other entry inhibitors have indicated that particular amino acid changes in the viral envelope protein are associated with increases in CD4+ T cell count [11].

It is our hypothesis that maraviroc has, by interference with CCR5 activation through its natural ligands or residual HIV, an inhibitory effect on the residual systemic immune activation in patients on HAART which relates to lower CD4+ T cell turnover and increased naive CD4+ T cell gain. This will result in a broader TCR repertoire and better immune competence in the long run.

# Hypothesis

Therefore maraviroc, by a yet unknown mechanism, stimulates immune recovery by increasing CD4+ cell count.

# 2. OBJECTIVES

Primary Objective: to confirm the hypothesis that maraviroc stimulates immune recovery by increasing the CD4+ cell count.

Secondary Objective: to explore, by virologic and immunologic investigations, the underlying mechanisms of this hypothesis.

## 3. STUDY DESIGN

## 3.1. General

The MIRS study is a double blind, randomized, placebo-controlled, multicenter exploratory mechanistic study in patients on HAART (in The Netherlands), that after a minimum of 6 months viral suppression (< 50 copies/ml) still have inadequate immune recovery. There will be two study groups (both with undetectable plasma HIV RNA): group one with CD4+ cells < 200 cells per µL and group 2 with CD4 cells between 200-350 CD4+ cells per µL. In both study groups, patients will be randomized to receive either maraviroc or placebo added to the current antiretroviral regimen. After randomization 50% of the patients will receive maraviroc, the remaining 50% placebo. The dose of maraviroc will be adjusted to the co-medication the study subjects are taking (because of farmacokinetic interactions), from 150 mg BID to 600 mg BID according to instructions in the "summary of product characteristics (SPC)" of maraviroc. The duration of study will be one year (48 weeks). Each visit (see below for schedule) blood will be drawn for CD4+ cell count (procedure to be performed in local laboratory at study site). Also, each visit 30 ml of heparin blood en 10 ml of EDTA blood will be drawn for immunologic en virologic studies. All other blood investigations are to be decided on and performed by the treating physician according to standard of care. Furthermore, each visit study subjects will be asked for any adverse events, vital signs will be recorded and physical examination will be performed. At the screening visit and at the end of study visit a complete physical examination will be performed.

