# 4.4 Sample size calculation

Sample size calculation was based on an expected difference in rise in CD4 cells of 30% in the treatment group compared with placebo. For this calculation an estimated CD4 cell increase of 10% in the placebo group was used. Estimated standard deviations of CD4 cells are 40% and 30% in the treatment group and placebo group, respectively.

We used an alpha=0.05 and beta=0.10 (power is 0,90). According to this calculation 124 study subjects are needed (62 in the treatment group, 62 in the placebo group). Anticipating a small loss of follow-up, we aim to include 130 patients.

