# 7. METHODS

# 7.1 Study parameters/endpoints

# 7.1.1 Main study parameter/endpoint

A 30% increase of the amount CD4+ cells in the treatment group compared with the placebo group (for both study groups).

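### The main endpoint is set for both study groups, but the protocol gives one total and one comparison with no number per group, so the stated 90% power belongs to no defined primary test

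*Protocol*

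**What the plan says.** Section 3.1 defines study group one (CD4 below 200) and study group two (CD4 200 to 350), and states "In both study groups, patients will be randomized to receive either maraviroc or placebo added to the current antiretroviral regimen". Section 7.1.1 then gives the main endpoint as "A 30% increase of the amount CD4+ cells in the treatment group compared with the placebo group (for both study groups").

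Section 4.4 does not mention the study groups. It says "Sample size calculation was based on an expected difference in rise in CD4 cells of 30% in the treatment group compared with placebo", adds "For this calculation an estimated CD4 cell increase of 10% in the placebo group was used", and gives the spread: "Estimated standard deviations of CD4 cells are 40% and 30% in the treatment group and placebo group, respectively". The error rates are "We used an alpha=0.05 and beta=0.10 (power is 0,90"). The result is "According to this calculation 124 study subjects are needed (62 in the treatment group, 62 in the placebo group"), followed by "Anticipating a small loss of follow-up, we aim to include 130 patients".

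Section 9.3 plans an intention-to-treat repeated measures and regression analysis of whether CD4 develops differently over time in the treated and control arms. It does not mention study group. Neither do the endpoint in the Summary, the primary objective in section 2, or the randomisation text in section 7.2. Section 9.5 refers to a separate statistical analysis plan, which is not at hand.

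**The concern.** A reader cannot tell which test decides the trial. The endpoint wording in 7.1.1 points to a result in each study group. The wording of 4.4 and 9.3 points to one comparison of all treated against all control patients. The two designs have different power at the same 124 patients, and only one of them needs a number per group.

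If the claim is made per group, the power of each test depends on how recruitment divides between the strata, and nothing in the protocol fixes that. An analysis plan written later can name the test, but it cannot supply patients to a stratum that recruited too few. If the claim is pooled, the endpoint wording is wrong and the stated power does not describe the test. Either way, the 90% on which the trial was justified is not tied to a defined primary claim.

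**Working it through.** **Inputs.** From section 4.4: SDs of 40 (maraviroc) and 30 (placebo) percentage points, alpha 0.05, power 0.90, placebo rise 10%, 62 per arm. From section 3.1: 1:1 allocation. Assumptions: alpha is two-sided (not stated), and the outcome is a simple two-group comparison of mean percentage rise. The effect is read in two ways: a 30-point difference (40% against 10%) or a 20-point difference (30% against 10%). A relative reading (13% against 10%, 3 points) would need about 5,838 patients and is ruled out.

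**Formulas.** Variance term: 40² + 30² = 2,500. Normal approximation per arm: n = (1.960 + 1.282)² × 2,500 / d², with (1.960 + 1.282)² = 10.51. Power: noncentral t with 2n − 2 degrees of freedom and noncentrality d / √(2,500/n).

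**Reproducing the 124.**

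| Difference | Normal, per arm | t-test, per arm | Total for one comparison | Twice that (t-test) |
|---|---|---|---|---|
| 30 points | 10.51 × 2,500/900 = 29.2, so 30 | 31 | 60 to 62 | **124** |
| 20 points | 10.51 × 2,500/400 = 65.7, so 66 | 67 | 132 to 134 | 268 |

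At 30 points, 30 per arm gives 89.8% and 31 per arm gives 90.8%, so 31 is the smallest sufficient number. Two groups of 62 make 124 exactly. No single pooled comparison gives 124, and one-sided and 80%-power variants do not either.

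**Power at the stated 62 per arm, one pooled test.**
- 30 points: noncentrality 30/√(2,500/62) = 30/6.35 = 4.72; power 99.7%.
- 20 points: noncentrality 20/6.35 = 3.15; power 88%.

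**Power if each group is tested at 0.05 and both must succeed.** The groups hold different patients, so the two powers multiply. Assume an equal split, 31 per arm in each group.
- 30 points: noncentrality 30/√(2,500/31) = 30/8.98 = 3.34; 91% per group; joint 0.908² = 82%.
- 20 points: noncentrality 20/8.98 = 2.23; 59% per group; joint 0.591² = 35%.

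**An uneven split.** Take 40 and 84 patients, for illustration only. At 30 points the smaller group (20 per arm) has 74% power and the larger (42 per arm) 97%; joint 0.744 × 0.970 = 72%.

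**What 90% joint power would need.** Each group needs power √0.90 = 94.9%. At 30 points, (1.960 + 1.632)² × 2,500/900 = 35.8, so 36 per arm per group, or 144 in total (normal approximation).

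**The case against.** The strongest reply is that the size is sound and only its explanation is missing. The total equals two groups of 62, which fits the two randomised groups in 3.1 and the endpoint wording in 7.1.1. On that view section 4.4 merely fails to say that it sized each group and added them. This largely stands: it is the likeliest origin of the number, and it means that pooling should not be imposed on the sponsor as the only remedy. It remains an inference. Even if it is right, the 90% holds per group and only under an equal split, which the protocol does not require.

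A second reply is that a study-group term, an interaction test or a multiplicity rule may be in the analysis plan. That also stands, and the silence of section 9.3 is not by itself a fault. The endpoint's scope, the sample size and the number per group, however, are protocol matters, and here they do not agree.

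Three stronger readings are tempting and are not supported:
- A reader might infer that the type I error is inflated to 1 − 0.95² = 9.75%. That needs a rule under which success in either group suffices, each tested at 0.05. No section says this, and the wording of 7.1.1 points the other way. If both groups must succeed, the error is not inflated.
- A reader might infer that 4.4 was calculated for a pooled comparison. Its wording suggests so; its arithmetic does not.
- A reader might infer that leaving out study group makes the standard error invalid. The documents do not say whether randomisation is stratified, and omitting a stratum generally makes the test conservative.

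**Conclusion.** The point holds as an inconsistency between sections 7.1.1, 4.4 and 9.3. The stated 90% is right only for separate tests in two equally filled groups at a 30-point difference, and the protocol states neither the separate tests nor the equal split. For the claim as a whole, power at 124 patients is 99.7% if pooled and 82% if both groups must succeed at 30 points; at 20 points the figures are 88% and 35%. An uneven split lowers the joint figure further, to about 72% in the 40/84 illustration.

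These figures rest on a two-sided alpha, the same effect and SDs in both groups, and a simple comparison of means; the planned repeated measures analysis could have different power. The correction should be made, but it does not imply that the trial is too small or that its error rate is uncontrolled.

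**What to change.** State one primary test and make sections 7.1.1, 4.4 and 9.3 agree on it, with the effect given in percentage points. Two routes are open:

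- **(a) Pooled.** One test at two-sided 0.05, stratified by study group. Report the group effects and the arm-by-group interaction as secondary, with confidence intervals. Remove the reference to both study groups from the main endpoint and restate the power (99.7% at 30 points, 88% at 20).
- **(b) Per group.** If the sizing was indeed by group, say that 124 is 31 per arm in each group, fix a number per group within the 130 (for example 65 each), and state the success rule. If both groups must succeed, give the joint power of about 82%. If either suffices, split the alpha; at 0.025 per group the per-group power for 30 points is about 86% (normal approximation).

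In both cases make study group a stratum on the pharmacy's randomisation list and a factor in the model.

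The cost is protocol wording and one stratum on the list. Route (b) also means a less favourable stated power, and a target per group may slow recruitment of the scarcer stratum.

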# 3.2 Flow chart

Procedure	Screen	Baseline	Week 2,	Week 48	Follow up visit
		(day 1)	4, 8, 12,	(end of	after early
			24, 36	study) or	termination
			(interim	early	study
			visits)	termination	(4 weeks)
				visit	
Randomization		Х			
Informed Consent	Х	Х			
and Eligibility Check					
Medical History	Х				
Physical Exam / Vital	Х			Х	
Signs / weight					
Pregnancy test	Х				
Targeted Physical			Х		
Exam / Vital Signs /					
weight					
Adverse Events		Х	Х	Х	
Concomitant	Х	Х	Х	Х	Х
Medications					
CD4+ cell count 	Х	Х	Х	X	X
Plasma HIV RNA 	Х		Only: week	Х	Х
			4, week		
			12, week 24 and		
			week 36		
EDTA (virologic	Х	Х	Х	x	x
studies) 					
Heparin blood		Х	Х	Х	Х
(immunologic and					
virologic studies) 					
Dispense Study		Х	Х		
Medication					
Collect all study				X	
medication					

1. CD4+ cell count to be performed in local laboratory at study site

2. 1 tube (each 10 ml) EDTA blood. Plasma HIV RNA will be performed at the site laboratory at screening, week 12, week 24, week 36 and week 48 (or early termination visit).

Depending on local laboratory logistics, in certain sites the 10 ml EDTA blood that will be drawn for virological studies will be partly used for this purpose; in other sites extra EDTA blood (4.5 ml) will have to be drawn at these visits.

3. 3 tubes (each 10 ml) heparin blood

# 4. STUDY POPULATION

## 4.1 Population (base)

The populations of interest for this study are those patients infected with HIV-1 in which treatment with HAART did not result in an adequate immunological response despite viral suppression (the so called "immunological non responders"). The study subjects will be recruited from a potential study population of approximately 550 known patients in the Netherlands ([name], SHM, personal communication).

## 4.2 Inclusion criteria

-Age 18 years or older

-HAART with a maximal treatment interruption of two weeks -viral suppression (< 50 copies/ml) for 6 months

And either:

-CD4+ count < 200 cells/mm3 after minimal one year of treatment with HAART (study group one)

## Or:

-a CD4+ cell count between 200 and 350 cells/mm3 after minimal two years of treatment with HAART (studygroup two)

## 4.3 Exclusion criteria

-Previous use of maraviroc

-HIV-2 infection

-HAART consisting of a combination of tenofovir and didanosine

-Active infection for which antimicrobial treatment

-Acute hepatitis B or C

-Chronic hepatitis B or C for which treatment with (peg)interferon and/or ribavirine

(Note: patients with untreated chronic hepatitis B or C can be included)

-Immunosuppressive medication

-Radiotherapy or chemotherapy in the past 2 years

-Pregnancy or breastfeeding an infant

-Subjects with known hypersensitivity to maraviroc or to peanuts, or any of its excipients or dyes as follows:

- Excipiens from tablet: microcrystalline cellulose, dibasic calcium phosphate (anhydrous), sodium starch glycolate, magnesium stearate.
- Film-coat: [Opadry II Blue (85G20583) contains FD&C blue #2 aluminium lake, soya lecithin, polyethylene glycol (macrogol 3350), polyvinyl alcohol, talc and titanium dioxide.

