# 5.2 Use of co-intervention

- 1. Maraviroc will be added tot the antiretroviral regimen the study subject is already taking.
- 2. If necessary for clinical reasons, the antiretroviral regimen can be changed at the discretion of the treating physician.
- Maraviroc is a substrate for CYP3A4 inhibition. The dose of maraviroc has to be adjusted if other medication is co-administered that induces or inhibits CYP3A4 metabolism (see SPC).

- 4. The concomitant use of maraviroc and St. John's wort or products that contain St. John's wort is not recommended (St. John's wort is expected to decrease maraviroc concentration to suboptimal levels).
- 5. Patients are advised to use adequate contraception, since there are no data in humans with respect to the potential teratogenicity of maraviroc.

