## 7.3 Study procedures

## 7.3.1 Study visits and procedures

An overview of the schedule of study visits and procedures is presented as a flowchart (see paragraph 3 "study design").

Study subjects will be asked to visit the outpatient clinic for study visits. There will be nine visits during the study: screenings visit, baseline visit, 6 interim visits and end of study visit. Assuming the patient would perform a visit on the outpatient clinic every three months if he was not participating in this study, this means 5 extra visits to the outpatient clinic. Each study visit CD4+ cell count will be performed in the local laboratory at the study site (2 ml EDTA blood). Also, each visit (except screeningsvisit) 40 ml blood (10 ml EDTA blood and 30 ml heparin blood) will be drawn by venapunction for immunologic and virologic studies. Taken into account that the blood investigations performed as part of this study will partly replace the investigations the treating physician would otherwise anyway perform, this would mean that maximum approximately 322.5 ml blood per study subject will be drawn extra for studypurposes during the study period (48 weeks). If a patient has to be withdrawn from the study and a follow up visit is needed, then an additional 42 ml of

blood will have to be drawn (30 nl for immunological investigations, 10 ml for virological investigations and 2 ml for CD4+ cell count). The blood samples will be transported to the central site (UMC Utrecht) for further analysis. Each visit (except baseline) patients will be questioned for adverse events. Vital signs and weight will be recorded, and, if necessary, targeted physical examination will be performed (to detect changes compared with baseline). Complete physical examination will be performed at baseline and end of study visits. At baseline and interim visits the study medication will be dispensed. Dosing adherence will be assessed (by counting) and drug accountability will be performed at interim and end of study visits

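### The only pregnancy test is at screening, with no limit on the time to baseline, so randomisation and first dispensing require no recent negative result

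*Protocol*

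**What the plan says.** Section 4.3 of the protocol excludes "Pregnancy or breastfeeding an infant". The criterion names no test and no time.

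The flow chart in section 3.2 has a row "Pregnancy test" with a single mark, in the Screen column. The row for consent "and Eligibility Check" is marked at both Screen and Baseline. Randomisation is marked at Baseline (day 1).

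Section 5.2 states: "Patients are advised to use adequate contraception, since there are no data in humans with respect to the potential teratogenicity of maraviroc".

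Section 7.3.1 treats screening and baseline as separate visits: "There will be nine visits during the study: screenings visit, baseline visit, 6 interim visits and end of study visit". It also places the first supply of study drug at baseline: "At baseline and interim visits the study medication will be dispensed". Neither this section nor any other part of the protocol says how long after screening the baseline visit may take place.

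**The concern.** An exclusion protects a patient only if it is verified close to the moment of exposure. Here the test belongs to one visit and the exposure to a later one, with no stated limit on the gap. A pregnancy that begins around or after screening can pass the day-1 eligibility check unless the woman knows of it and says so, or the site tests on its own initiative.

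What is at stake is exposure of an early pregnancy to a drug for which the protocol itself reports no human teratogenicity data, and where contraception is advised but not required. The deuterated-water substudy (section 7.3.3, about 10 subjects) relies on the same single test: it recruits on the main trial's criteria and adds no pregnancy test of its own.

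The sections do not contradict one another. The weakness lies in the schedule that they fix.

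**Working it through.** **The schedule, side by side**

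| Item | Screen | Baseline (day 1) | Later visits |
|---|---|---|---|
| Pregnancy test (3.2) | yes | no | no |
| Eligibility check (3.2) | yes | yes | no |
| Randomisation (3.2) | no | yes | no |
| Dispensing (3.2, 7.3.1) | no | yes | interim visits |

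Pregnancy tests scheduled: one. Tests at baseline or later: none. Stated limit on the screening-to-baseline interval: none. The flow chart was read from a PDF, but the column is clear: the pregnancy-test mark sits where the medical-history mark sits (Screen only), and the randomisation mark is one column further on.

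**Size**

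The protocol has no figure of its own to reproduce, and gives no number of women, interval or pregnancy rate. The inputs are:

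- Women of child-bearing potential among the 130 planned subjects: 20 to 40 (assumption; the 130 is from section 4.4).
- Interval from screening to baseline: 4 to 8 weeks (assumption).
- Pregnancies per woman per year: 2% to 5% (assumption).
- Share on maraviroc: one half (section 3.1: "After randomization 50% of the patients will receive maraviroc, the remaining 50% placebo").

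Step 1, risk per woman in the interval = yearly rate × weeks / 52:
- Low: 2% × 4/52 = 0.154%
- High: 5% × 8/52 = 0.769%

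Step 2, expected pregnancies at first dose = number of women × risk:
- Low: 20 × 0.154% = 0.031
- High: 40 × 0.769% = 0.308

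Step 3, on maraviroc = half of step 2:
- Low: 0.015
- High: 0.154

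Step 4, extreme case with all 130 subjects in this group: 130 × 0.769% = 1.0 at first dose, of which 0.5 on maraviroc. This is a ceiling for the assumed rates and intervals, not a realistic case.

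Step 5, a shorter gap of 1 to 2 weeks, which the protocol equally allows: 20 × 2% × 1/52 = 0.008 to 40 × 5% × 2/52 = 0.077, half of that on maraviroc.

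As a count of pregnancies that go unnoticed, these figures err high, because some women would know and report it. In the other direction, the protocol does not cap the interval at 8 weeks, and the risk grows in proportion to it.

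**What a baseline test would leave uncovered**

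Over the 48 treatment weeks the risk per woman is 2% × 48/52 = 1.85% to 5% × 48/52 = 4.62%. At the same yearly rate this is 48/8 = 6 to 48/4 = 12 times the risk before first dose.

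**The case against.** The best defence is that the exclusion is applied again on day 1. The flow chart repeats the eligibility check at baseline, so the investigator must consider pregnancy afresh at randomisation, with the contraception advice in section 5.2 as a further safeguard. Section 5.2 also reports an absence of data, not a known harm, and maraviroc is a registered product whose risks the protocol refers to the SPC. On this view a second test is a preference, the expected number is close to nil on inputs that are all assumed, and the proposal deals with the smaller part of the risk: taking the interval and the treatment period together, 48/56 = 86% to 48/52 = 92% falls after first dose.

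Much of this is fair. The number is small, the inputs are assumptions, and on-treatment exposure is the larger share. The repeated eligibility check is a real safeguard against a pregnancy that is known. It does not help with one that is unknown, because no test is attached to it. The SPC and the patient letter are not at hand and cannot be assumed to fill the gap; the protocol's references to the SPC concern product information, dosing and interactions and set no test time for this trial. That a larger risk exists later is no reason to leave the entry check unverified when verifying it costs so little.

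**Conclusion.** The point holds as a modest, inexpensive improvement to patient safety that the sponsor should make. As written, the protocol requires no pregnancy test at randomisation and first dispensing, nor within any set time of them. That conclusion rests on the text alone.

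Its size rests on assumptions: 0.03 to 0.31 expected pregnancies at first dose and 0.015 to 0.15 on maraviroc, with zero the most likely count. Confidence that the matter is of practical weight is moderate, because the number of women and the usual gap between visits are unknown. Neither the sample size nor the primary analysis is affected.

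**What to change.** In the flow chart (section 3.2), add a cross for the pregnancy test in the Baseline (day 1) column for women of child-bearing potential. Add one sentence that a negative result is required before randomisation and dispensing. Alternatively, state a short maximum interval from screening to baseline, beyond which the test must be repeated.

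The cost is one cross, one sentence, one inexpensive test per woman concerned and a short wait for the result. Blood is already taken at that visit: "Also, each visit (except screeningsvisit) 40 ml blood (10 ml EDTA blood and 30 ml heparin blood) will be drawn by venapunction".

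The change narrows the gap without closing it. A very recent conception can still be missed, and the 48 treatment weeks are not covered.
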